11.9.9 Serious Adverse Events

An **Adverse Event or Suspected Adverse Reaction** is considered “serious” if, in the view of either the investigator or sponsor, it results in any of the following outcomes:

- Death;
- A life threatening adverse event; (Note: the term “life-threatening” as used here refers to an event in which the patient was at risk of death at the time of the event; it does not refer to an event which hypothetically might have caused death if it were more severe);
- In-patient hospitalization or prolongation of existing hospitalization;
- A persistent or significant disability/incapacity (substantial disruption of the ability to conduct normal life functions);
- A congenital anomaly/birth defect;
- Any “other” important medical event.

Important medical events that may not result in death, be life-threatening or require hospitalization may be considered Serious Adverse Events when, based on appropriate

medical judgment, they may jeopardize the patient and may require medical or surgical intervention to prevent one of the outcomes listed in this definition.

Regardless of the above, any additional adverse events which the Principal Investigator considers significant should be immediately reported to the Contract Research Organization [REDACTED].

Any Serious Adverse Event, whether deemed drug-related or not, must be reported by the Investigator to the Contract Research Organization [REDACTED] Project Manager by telephone **within 24 hours** after the Principal Investigator or Study Coordinator becomes aware of its occurrence. The Principal Investigator or the Principal Investigator's Designee must complete a Serious Adverse Event (SAE) Form and fax it to the Contract Research Organization [REDACTED], along with the patient's Adverse Events Log and Concomitant Medications Log **within 24 hours** of notification of the event. The CRO [REDACTED] must notify the Medical Monitor, Actavis Study Manager and Actavis's Drug Safety Department **within 24 hours** of the initial notification of the event. When appropriate, the Actavis's Drug Safety Department will notify the U.S. Food and Drug Administration (FDA) of drug related Serious Adverse Events.

Documentation should be sent to the CRO Study Manager and Actavis's Drug Safety Department listed below:

CRO Study Manager	Medical Monitor	Sponsor Study Manager	Drug Safety Department
[REDACTED]	[REDACTED]	Actavis. [name]	Actavis Pharmacovigilance [REDACTED]

The Principal Investigator or the Principal Investigator's Designee must be prepared to supply the Medical Monitor with the following information:

- a. Principal Investigator name and Site Number
- b. Patient I.D. Number
- c. Patient initials and date of birth
- d. Patient demographics
- e. Clinical event
 - 1) Description
 - 2) Date of onset
 - 3) Severity
 - 4) Treatment (including hospitalization)
 - 5) Relationship to study drug
 - 6) Action taken regarding study drug
- f. If the AE was fatal or life-threatening
 - 1) Cause of death (whether or not the death was related to study drug)

- 2) Autopsy findings (if available)
- 3) Death Certificate

The Sponsor must notify FDA as soon as possible, but no later than 7 calendar days for a fatal or life threatening adverse event. The Sponsor must notify FDA and all participating investigators within 15 calendar days for any drug-related serious adverse events observed during the conduct of the study.

The Principal Investigator must provide a follow-up written report within 5 calendar days of reporting the event to the CRO. The written report must contain a full description of the event and any sequelae. Patients who have had an SAE must be followed clinically until all parameters (including laboratory) have either returned to normal or are stabilized. The Investigator must also report follow-up information if it becomes known to the Investigator. Actavis Study Manager and Actavis Drug Safety Department must receive any follow-up **within 24 hours** of receipt by Medical Monitor.

Reports of all SAEs must be communicated as soon as possible to the appropriate Institutional Review Board (IRB) or Independent Ethics Committee (IEC) and/or reported in accordance with local laws and regulations.

12 STATISTICAL METHODS

12.1 Sample Size Rationale

The sample size for this protocol is based on published data (Finacea® Summary Basis of Approval); Finacea® produced a percent reduction for inflammatory lesions of approximately 55% and the vehicle had a percent reduction of 40% after 12 weeks of treatment.

The anticipated standard deviation for inflammatory lesions is < 47%. A sample size of $n_1 = 280$, $n_2 = 280$ and $n_3 = 280$ evaluable mITT patients (1:1:1 ratio) to provide at least 224 PP patients in each of the Test and Reference treatment groups should provide at least an [REDACTED] probability of showing that, the 90% confidence interval on the Test/Reference ratio of percent reduction from baseline is contained within the interval 0.800 to 1.250 in the PP population and at the same time demonstrating that the Test and Reference products are superior to the vehicle in the mITT population.

In this study, enrolled patients will be randomized in the ratio of 1:1:1 to test, reference and vehicle treatments. It is anticipated that 75% of the mITT patients will qualify for the PP population. Accordingly, approximately 924 patients will be randomized in the study to obtain at least 840 mITT patients in a 1:1:1 ratio (280:280:280 patients, respectively) to each treatment group.

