3.2 Sample Size

The sample size for this protocol is based on published data (Finacea® Summary Basis of Approval); Finacea® produced a percent reduction for inflammatory lesions of approximately 55% and the Vehicle had a percent reduction of 40% after 12 weeks of treatment.

The anticipated standard deviation for inflammatory lesions is < 47%. A sample size of n1 = 280, n2 = 280, and n3 = 280 evaluable mITT patients (1:1:1 ratio) to provide at least 224 PP patients in each of the Test and Reference treatment groups should provide at least an [REDACTED] of showing that, the 90% confidence interval on the Test/Reference ratio of percent reduction from baseline is contained within the interval 0.800 to 1.250 in the PP population and at the same time demonstrating that the Test and Reference products are superior to the vehicle in the mITT population.

In this study, enrolled patients will be randomized in the ratio of 1:1:1 to test, reference and vehicle treatments. It is anticipated that 75% of the mITT patients will qualify for the PP population. Accordingly, approximately 924 patients will be randomized in the study to obtain at least 840 mITT patients in a 1:1:1 ratio (280:280:280 patients, respectively) to each treatment group.

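### At the stated SD limit of 47, the design meets all three primary criteria with probability about 0.70 (224 PP per arm) or 0.66 (the 210 implied by the plan's 75% rate), so the power statement needs its SD, true ratio and PP size

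*Protocol*

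**What the plan says.** Protocol 12.1 sets out the planning assumptions, and SAP 3.2 repeats them.

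- Reference: "Finacea® produced a percent reduction for inflammatory lesions of approximately 55" per cent.
- Vehicle: "the vehicle had a percent reduction of 40% after 12 weeks of treatment".
- Spread: "The anticipated standard deviation for inflammatory lesions is < 47" per cent. This is an upper limit; no point value is given.
- Size: 280 per arm, described as "evaluable mITT patients (1:1:1 ratio) to provide at least 224 PP patients in each of the Test and Reference treatment groups".
- Claim: this size "should provide at least an [REDACTED] probability" (protocol) or "should provide at least an [REDACTED] of showing that" (SAP) of placing the 90% interval for the Test/Reference ratio within 0.800 to 1.250 in the PP population while both actives beat vehicle in the mITT population. The number is blacked out in both documents.
- PP rate: "It is anticipated that 75% of the mITT patients will qualify for the PP population".

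Neither section states a mean for the Test product or a true Test/Reference ratio. Fieller's method for the interval is specified in protocol 12.5.1 and SAP 7.5.2.1. SAP 6.3 makes the PP population definitive for equivalence, and SAP 6.2 makes the mITT population definitive for superiority.

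**The concern.** A probability promised as a minimum, under an SD stated only as a ceiling, should hold up to that ceiling. All the inputs except the true ratio are legible, so the probability can be recomputed at the ceiling. It comes out well below the level usually sought for a pivotal equivalence trial.

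The PP size adds to this. The probability rests on 224 PP patients per arm, but the next paragraph anticipates a PP rate that yields fewer.

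At stake is what a reader can conclude from a failed result. At SD 47, two identical products would miss the equivalence limits in about 28% of trials, and would miss at least one of the three criteria in about 30%. Anyone interpreting the outcome needs to know the conditions under which the planned probability was calculated.

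**Working it through.** **The plan's own figure.** It is redacted, so it cannot be reproduced. What follows is a recomputation from the legible inputs.

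**Inputs** (protocol 12.1 and SAP 3.2 unless noted)
- Mean reductions: Reference 55, Vehicle 40.
- Test 55, so a true ratio of 1. This is my assumption.
- Common SD 47, the stated limit.
- PP 224 per arm and mITT 280 per arm, with the PP set nested in the mITT set.
- Superiority at two-sided 0.05 without multiplicity adjustment (protocol 12.3).
- Site terms ignored.

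**Equivalence, 224 PP per arm.** The 90% Fieller interval lies within [0.80, 1.25] when T − 0.8R and 1.25R − T are both significantly positive at one-sided 5%.
- SE of one mean: 47/√224 = 3.140.
- T − 0.8R: expected value 55 − 44 = 11; SE 3.140 × √(1 + 0.64) = 4.022; ratio 11/4.022 = 2.735.
- 1.25R − T: expected value 68.75 − 55 = 13.75; SE 3.140 × √(1 + 1.5625) = 5.027; ratio 2.735.
- Critical t on 446 df: 1.648.
- Each side passes with probability Φ(2.735 − 1.648) = Φ(1.087) = 0.861.
- The two sides practically never fail together, so the probability is 2 × 0.8615 − 1 = **0.723**. Simulation agrees.

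**Superiority, 280 mITT per arm**
- SE of a difference: 47 × √(2/280) = 3.972; 15/3.972 = 3.776.
- Each test: Φ(3.776 − 1.964) = 0.965.
- Both tests, sharing the vehicle arm: 0.937 by simulation.

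**All three criteria.** Simulation gives **0.695**. Treating equivalence and superiority as independent would give 0.723 × 0.937 = 0.677. The joint figure cannot exceed the 0.72 for equivalence alone.

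**PP size implied by the 75% rate**
- 0.75 × 280 = 210 per arm, whereas 224/280 = 80%.
- In total, 0.75 × 840 = 630, against the 672 PP patients given in protocol 11.2 and SAP 3.1.
- With 210: SE 47/√210 = 3.243; 11/(3.243 × √1.64) = 2.648; Φ(2.648 − 1.649) = 0.841; equivalence 2 × 0.841 − 1 = **0.68**. All three criteria: **0.66**.

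**Dependence on the SD** (224 PP and 280 mITT per arm, true ratio 1)

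| SD | Equivalence | All three |
|---|---|---|
| 47 | 0.72 | 0.70 |
| 46 | 0.75 | 0.72 |
| 45 | 0.77 | 0.75 |
| 44 | 0.80 | 0.78 |
| 43 | 0.82 | 0.81 |
| 42 | 0.84 | 0.83 |
| 41 | 0.86 | 0.85 |
| 40 | 0.88 | 0.88 |

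The joint probability reaches 0.80 at an SD of about 43.2 and 0.85 at about 41. With 210 PP per arm, 0.80 needs an SD of about 42.

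**Dependence on the true ratio** (SD 47, 224 PP). The joint probability is 0.66 at a ratio of 0.98 and 0.55 at 0.95. It is 0.70 when Test is 56 (ratio 56/55 = 1.02) and 0.66 at 1.05. A ratio of 1 is therefore close to the best case.

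**Where about 80% appears at SD 47.** If all 280 mITT patients per arm are counted in the equivalence test, equivalence is 0.84 and the joint figure is 0.81. The text ties equivalence to the PP population, so that is not the stated design.

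**The case against.** The strongest reply is that no error can be shown against a number nobody can see. The redaction is not a fault of the plan, and the only textual clue is the article *an* before the gap, which suits a figure in the eighties but proves nothing. The SD is a strict upper limit, so the sponsor may have calculated at a lower value. At 43 or below, the planned 224 and 280 per arm give 80% or more, which agrees with the text. The true ratio of 1 is supplied here and is not in the plan. The PP size is also stated as a minimum.

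Most of this stands. A reader might infer that the plan claims eighty-something per cent and fails to deliver it, or that the sponsor put the mITT count into the equivalence calculation. The documents support neither reading, because the claimed figure, the SD used and the method of calculation are not visible. Nor do they show that a failed result would be taken as a product difference.

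Three things survive:
- A minimum attached to an SD range should hold across that range. A figure of 80% or more would not hold between about 43 and 47.
- The assumed ratio does not exaggerate the problem, since it is close to the most favourable value.
- The stated minimum is the size on which the promise rests. For scale, 80% at SD 47 would take about 265 PP per arm (about 330 mITT at an 80% PP rate).

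The mismatch between 75% and 224 does not depend on the hidden figure.

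**Conclusion.** The point holds in two parts.

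**Conditional.** At the SD limit of 47, a true ratio of 1, and 224 PP and 280 mITT patients per arm, the probability is about 0.72 for equivalence and about 0.70 for all three criteria. If the hidden figure is 80% or more, it is valid as a minimum only for SDs up to about 43 (about 41 for 85%). Whether it is that high cannot be settled from the documents.

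**Unconditional.** The expected 75% PP rate gives 210 per arm and contradicts the 224 on which the probability rests. At SD 47 this lowers the two probabilities to about 0.68 and 0.66.

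The calculation assumes normal data, a common SD in all arms, PP patients nested in mITT and no site effect. It does not show that the trial is too small, because the true SD may be well below 47.

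**What to change.** In protocol 12.1 and SAP 3.2:

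1. Reconcile the 75% PP rate with 224 PP patients per arm. Either the rate is 80%, or the PP size is 210 per arm and the PP totals elsewhere change with it.
2. State the probability together with the SD, the true Test/Reference ratio, the PP size and the method used. Two forms would be correct at a true ratio of 1:
   - about 70% for all three criteria at SD 47 with 224 PP per arm (about 66% with 210); or
   - the claimed figure with the lower SD it requires. For 80%, that is about 43 with 224 PP per arm, or about 42 with 210.

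The sponsor knows the hidden figure and the SD behind it, and can tell at once which form applies. If the calculation already used an SD of about 43 or less, the second form records it, and the lower SD should be justified from the source data.

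This is a change of wording only, with no extra patients and no change to the analysis. The cost is a less favourable stated probability, or a commitment to a smaller SD.

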8 SYNOPSIS

Protocol number:	
Title of Study:	A Multicenter, Double-blind, Randomized, Parallel-group, Vehicle-Controlled Study to Evaluate the Safety and Clinical Equivalence of a Generic Azelaic Acid Foam, 15% and the Reference Listed Finacea® (azelaic acid) Foam, 15% in Patients with Moderate Facial Rosacea
Sponsor:	Actavis Laboratories UT
Test Product:	Azelaic Acid, 15% topical foam (Actavis Laboratories UT)
Reference Product:	Finacea® (Azelaic acid) Foam, 15% (Bayer HealthCare)
Vehicle:	Foam Vehicle of the test product (Actavis Laboratories UT)
Objectives:	To compare the safety and efficacy profiles of a generic Azelaic Acid Foam, 15% to the reference listed Finacea® (azelaic acid) Foam, 15% and to demonstrate therapeutic equivalence and safety of the two active foams in the treatment of moderate facial rosacea, and to demonstrate superiority of the reference and test products over the vehicle.
Study Design:	This is a randomized, vehicle-controlled, parallel-group, multicenter, double-blind study of Azelaic Acid Foam, 15% and the reference listed Finacea® (azelaic acid) Foam, 15% in patients with moderate facial rosacea.
Number of Study Centers:	Approximately 26 centers
Duration of Patient Participation:	Each patient will participate in the study for approximately 12 weeks from the time the patient signs the Informed Consent Form (ICF) through date of the final contact with the subject. The study treatment period will last for 84 days (12 weeks).
Key Inclusion Criteria:	Healthy male and non-pregnant female patients aged \geq 18 years with a diagnosis of moderate facial rosacea will be selected to participate in the study. Moderate facial rosacea is defined as the presence of at least eight and not more than fifty inflammatory facial lesions (i.e. papules/ pustules) and the presence of persistent erythema and telangiectasia.
Dosage and Administration:	Randomized patients will apply the foam to the entire facial area (cheeks, chin, forehead, and nose) twice daily for 12 weeks.
Number of Patients:	Up to 1010 patients will be enrolled in the study to randomize 924 patients to obtain at least 840 mITT patients in a 1:1:1 ratio (280:280:280 patients, respectively) to each treatment group and 672 (224:224:224) evaluable subjects in PP population: 
 • Azelaic Acid, 15% topical foam (Actavis Laboratories UT) • Finacea® (azelaic acid) Foam, 15% (Bayer HealthCare) • Foam Vehicle of the test product (Actavis Laboratories UT)

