3. STUDY OVERVIEW

3.1 Study Design

Up to 1010 patients will be enrolled in the study to randomize 924 patients to obtain at least 840 modified Intent-to-Treat (mITT) patients in a 1:1:1 ratio (280:280:280 patients, respectively) to each treatment group and 672 (224:224:224) evaluable subjects in the Per protocol (PP) population. Patients will be assigned in a 1:1:1 ratio to treatment with the Test product, Azelaic Acid Foam, 15% (Actavis Laboratories UT), the Reference product,

Finacea® (Azelaic acid) Foam, 15% (Bayer HealthCare) or the Vehicle control (Actavis Laboratories UT) in this multicenter, double-blind, randomized, vehicle-controlled, parallel-group study.

The assigned Investigational Product (IP) will be self-applied topically to the entire facial area (cheeks, chin, forehead, and nose) twice daily for 84 consecutive days. The IP should be gently massaged into the affected areas on the face twice daily, in the morning and evening after the patient's face has been washed with a mild cleanser and patted dry with a soft towel. Patients will be required to use diaries to document study treatments, any missed treatments and the occurrence of all adverse events.

The duration of each patient's participation in the study will be 84 days. Scheduled study visits will include: Visit 1 (Baseline Visit, Day 0), Visit 2 (Day 28 ± 4 days), Visit 3 (Day 56 ± 4 days), and Visit 4 (End of Treatment, Day 84 ± 4 days). A window of ± 4 days will be considered acceptable for each scheduled visit following the baseline visit.

If the Principal Investigator determines that the patient's condition has worsened to the degree that it is unsafe for the patient to continue in the study, the patient may be discontinued from the study as a treatment failure and the patient may be treated using the standard care.

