6.3 Per Protocol Population (PP Population)

The PP population includes all mITT patients who apply 75% to 125% of the scheduled applications of the assigned product for 12 weeks, do not miss more than 6 consecutive applications, return for the 12-week evaluation within +/- 4 days OR have discontinued from the study due to lack of treatment effect (after completing at least 8 weeks of compliant study medication use), and have no protocol major violations.

Patients who are discontinued prematurely from the study due to lack of treatment effect after completing at least 8 weeks of compliant study medication use and without major protocol violations will be included in the PP population as treatment failures (i.e., non-responders) even if they do not have Week 12 evaluation within the visit window or at all. An LOCF approach will be used for imputing missing lesion counts in these PP patients and they will be considered as failures in the IGE evaluations.

Patients discontinued prematurely for other reasons (including those who discontinue due to lack of treatment effect with less than 8 weeks of treatment) will be excluded from the PP population, but included in the mITT population, using LOCF.

Patients can be additionally excluded from the PP population due to non-compliance, if the Investigator's and Sponsor's review of their dosing times suggests a clinically meaningful departure from a twice-daily dosing pattern.

For the purpose of determining the PP status of the patient, a "major protocol violation" is any patient or investigator activity that could have possibly interfered with the therapeutic administration of the treatment or the precise evaluation of the treatment efficacy.

The PP population will be considered as definitive for testing the clinical equivalence and as supportive while testing the superiority.

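### The stated 75% per-protocol rate gives 210 PP patients per arm from 280 mITT, not the 224 on which the equivalence power rests; 224 needs 80%

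*Protocol*

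**What the plan says.** Protocol 12.1 sets 280 patients per arm as "evaluable mITT patients (1:1:1 ratio) to provide at least 224 PP patients in each of the Test and Reference treatment groups". The next paragraph gives the expected conversion from mITT to PP: "It is anticipated that 75% of the mITT patients will qualify for the PP population". It then continues: "Accordingly, approximately 924 patients will be randomized in the study to obtain at least 840 mITT patients in a 1:1:1 ratio".

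SAP 3.2 repeats both statements, the 75% rate and the phrase "to provide at least 224 PP patients in each of the Test and Reference treatment groups".

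The total PP size appears elsewhere. The protocol synopsis (section 8) gives "672 (224:224:224) evaluable subjects in PP population", as do Protocol 11.2 and 11.3.1, and SAP 3.1 gives "672 (224:224:224) evaluable subjects in the Per protocol (PP) population". Sections 12.1 and 3.2 themselves state only the 224 for Test and Reference.

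On the role of this population, SAP 6.3 says: "The PP population will be considered as definitive for testing the clinical equivalence and as supportive while testing the superiority".

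**The concern.** The rate and the count describe the same step, from mITT to PP, and they disagree. A reader who takes 75% at face value expects 210 PP patients per arm; a reader who takes 224 expects a rate of 80%. The sentence after the 75% rate opens as a consequence of it, so 75% is presented as the basis for 840 mITT and 924 randomised. Working back from 224 PP, it does not lead there.

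The PP count drives the precision of the Test/Reference ratio, which is the study's main claim, and the power statement is conditional on 224. If 75% is the real expectation, the planned PP size is too high by 14 per arm, and a probability computed at 224 is higher than the same calculation gives at 210. If 80% is the real expectation, only the 75% sentence is wrong. The documents do not say which.

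**Working it through.** **Inputs.** From Protocol 12.1 and SAP 3.2: 280 mITT per arm (840 in all), at least 224 PP in Test and Reference, 75% conversion, 924 randomised, reductions of 55% (reference) and 40% (vehicle), SD below 47%, equivalence limits 0.80 to 1.25 on a 90% interval. From Protocol 8, 11.2 and 11.3.1 and SAP 3.1: 672 PP in all.

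**1. Can the plan's figure be reproduced?**
- At the stated rate: 0.75 × 280 = 210 per arm and 0.75 × 840 = 630. Short by 14 per arm and 42 overall.
- Rate implied by the counts: 224/280 = 672/840 = 0.80.
- Reading 75% as a share of the randomised: 0.75 × 308 = 231 and 0.75 × 924 = 693. Neither matches.
- Chance variation: if the true rate is 75%, the binomial probability that an arm of 280 yields 224 or more is 2.9%.

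**2. Working back from 224 at 75%.** 224/0.75 = 298.7, so 299 mITT per arm and 3 × 299 = 897. At the plan's mITT yield of 840/924, 897 × 924/840 = 986.7, about 987 randomised. The stated 280/840/924 corresponds to an 80% rate.

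**3. Effect on precision.** With everything else equal, the interval half-width grows by √(224/210) = 1.033, about 3%.

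**4. Effect on power.** Assumptions, since the plan gives no test mean or true ratio: ratio 1.0, means 55/55/40, normal data, PP a subset of the 280 mITT with the same mean and SD. The Fieller interval lies inside the limits when both T − 0.80R > t·s·√(1.64/n) and 1.25R − T > t·s·√(2.5625/n), where T and R are the Test and Reference means, n is the PP size per arm and s is the residual SD.

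Normal approximation at SD 47:
- n = 224: 11/(47√(1.64/224)) = 2.735. The upper limit gives the same value: 13.75/(47√(2.5625/224)) = 2.735. Power ≈ 2Φ(2.735 − 1.645) − 1 = 0.72.
- n = 210: 11/(47√(1.64/210)) = 2.648. Power ≈ 2Φ(2.648 − 1.645) − 1 = 0.68.

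Simulation with 400,000 trials per cell. The joint event adds two-sided 0.05 superiority tests of both actives against vehicle in 280 mITT per arm:

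| SD | Equivalence, 224 | Equivalence, 210 | Joint, 224 | Joint, 210 |
|---|---|---|---|---|
| 47 | 0.723 | 0.683 | 0.695 | 0.656 |
| 45 | 0.773 | 0.737 | 0.753 | 0.717 |
| 43 | 0.820 | 0.788 | 0.806 | 0.774 |
| 40 | 0.882 | 0.856 | 0.876 | 0.850 |

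With a true ratio of 0.95 the joint figures are 0.554 against 0.521 (SD 47) and 0.741 against 0.714 (SD 40). Using critical values with 25 fewer degrees of freedom, to allow for about 26 centres, changes the joint figures by 0.001 or less. Each superiority test alone has power of about 0.965 at SD 47 and does not depend on the PP size.

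**The case against.** Five points can be made for the plan.

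- **The chain may have another origin.** 224 × 1.25 = 280 and 840 × 1.10 = 924, both exactly, so each target may simply have been marked up by 25% and then 10%. This is a plausible origin, though only an inference. It does not rescue the 75%: a 25% mark-up is itself an 80% yield, and allowing for a 25% loss means dividing by 0.75.
- **The mITT count is a minimum.** If 896 of the 924 randomised (97%) reached mITT, 75% would give 672. But the plan expects 840, and Protocol 12.1 ties 224 to 280 per arm.
- **The power statement is a lower bound under an SD given only as an upper limit.** The stated minimum could therefore still be met with 210 per arm. This stands, and it is why no missed target is claimed.
- **The consequence is small.** No test, margin or population rule changes, and superiority in mITT is unaffected. If 80% was meant, one sentence in each document is wrong. This also stands, and it limits the weight of the point.
- **The power figures are illustrative.** PP drops non-compliers and most patients with carried-forward values, so its mean and SD may differ from mITT. That could move both columns of the table. It leaves the arithmetic untouched.

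**Conclusion.** The contradiction is real and is present in both governing documents: 75% of 280 is 210, while 224 requires 80%. The gap is 14 PP patients per arm, or 42 in all across the three arms; only the Test and Reference counts enter the equivalence test.

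If 75% is the true expectation, the cost is about 3% in interval width and about 2.5 to 4 points of joint probability, for true ratios of 1.0 or 0.95 and an SD between 40 and 47, under the assumptions listed above. There is no bias and no increase in the chance of a false equivalence claim. Because the target probability is blacked out and the SD is only bounded, it cannot be said whether the design falls short. The arithmetic depends on no assumption; the power figures do. It should be corrected because the affected figure is the size of the definitive equivalence population and the basis of the stated power.

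**What to change.** State one mITT-to-PP rate and its basis, then make every figure follow from it:

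- **If 75% is intended:** restate the PP size as 210 per arm in Protocol 12.1 and SAP 3.2, and as 630 (210 per arm) in Protocol 8, 11.2 and 11.3.1 and SAP 3.1.
- **If 80% is intended:** replace the 75% in Protocol 12.1 and SAP 3.2 and justify the higher rate. The 224 and 672 then stand.

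In either case, recompute the joint probability at the resulting PP size, give the test mean, true ratio and SD used, and restate the probability if it changes.

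The cost is a wording change in two documents and one power calculation; the stated PP size or probability may look slightly less favourable. No extra enrolment follows from the correction itself. Whether the sample size should change can be judged only against the sponsor's own target. Keeping 224 PP at a 75% rate would need 299 mITT per arm and about 987 randomised. At the plan's ratio of enrolled to randomised, 987 × 1010/924 is about 1,079 enrolled, above the stated ceiling of 1010.
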